ctDNA detection is associated with near inevitability of disease recurrence in triple negative breast cancer, and that ctDNA does not spontaneously clear from the blood.

There is also new evidence for immuno-oncology therapy in TNBC; in 2019, the FDA granted accelerated approval for atezolizumab in combination with nab-paclitaxel in the treatment of patients with unresectable locally advanced or metastatic triple negative breast cancer, based on the findings from the phase III double-blind Impassion132 trial (NCT02425891) [17], further reinforcing the potential benefit of the interventional treatment arm within the study.

Taking this new data into account, the c-TRAK TN Independent Data Monitoring Committee proposed that the observation arm of the study was no longer required and should be closed. Following implementation of protocol v6.0, any patient with a subsequent ctDNA positive result detected in the blood (including those that had already been randomised to observation and remain in ctDNA surveillance) will be given the option to commence pembrolizumab treatment. This recommendation was endorsed by the ICR-CTSU Breast Systemic Therapies Trial Steering Committee and protocol version 6.0 was amended to close randomisation within the trial, with all patients allocated to treatment intervention.

Novel primary endpoint of sustained clearance of ctDNA

Even in patients with triple negative breast cancer, the most aggressive of breast cancer subtypes, the risk of relapse after treatment of primary breast cancer is relative low. The BEATRICE study [16] recently reported an invasive disease free survival relapse at 3 years occurred in only 16% of patients in the control group. Consequently phase III studies are large, and costly, with BEATRICE recruiting 2591 patients.

In the c-TRAK TN study we propose a novel primary endpoint of sustained clearance of ctDNA, defined as 'Absence of detectable ctDNA or disease recurrence 6 months (24 weeks) after commencing pembrolizumab'. This endpoint is chosen as a surrogate endpoint of treatment efficacy, which is anticipated to correlate with long-term outcome. A very similar primary endpoint (comparison of circulating tumour cell (CTC) detection rate at week 18 between trastuzumab treatment arm and observational arm) has been used in other studies in the adjuvant setting (TREAT-CTC, NCT01548677: Efficacy Study of Herceptin to Treat HER2-negative CTC Breast Cancer).

Use ctDNA diagnostics for detection of MRD

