19.3. Endpoint definitions

19.3.1. **Primary Endpoints**

ctDNA surveillance

• Positive ctDNA detection by 12 and 24 months from start of ctDNA surveillance. This will be calculated as the proportion of patients with ctDNA positivity by each time point from those with assessment performed at that time point. Proportions will be presented with associated exact 95% confidence intervals.

Therapeutic component

 Absence of detectable ctDNA or disease recurrence 6 months (24 weeks) after commencing pembrolizumab. This will be calculated as the proportion of patients without either detectable ctDNA or disease recurrence 6 months after commencing pembrolizumab. Proportions will be presented with associated exact 95% confidence intervals.

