- 4) Association between ctDNA clearance and time to recurrence in the pembrolizumab group. The times from first ctDNA detection to recurrence event will be calculated using statistical techniques for time to event data and summarised separately for patients with and without sustained ctDNA clearance. If numbers allow, time to recurrence will be formally compared between those with and without ctDNA clearance using standard time to event methods.

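### Comparing time to recurrence by ctDNA clearance is circular: clearance already requires no recurrence to week 24, so clearers look better even if the ctDNA result means nothing

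*Protocol*

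**What the plan says.** Three parts of the protocol have to be read together.

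- **The endpoint.** Section 1.2.1 defines sustained clearance as "Absence of detectable ctDNA or disease recurrence 6 months (24 weeks) after commencing pembrolizumab". Section 19.3.1 confirms that both conditions must be met: "This will be calculated as the proportion of patients without either detectable ctDNA or disease recurrence 6 months after commencing pembrolizumab".
- **Its purpose.** Section 1.2.1 adds: "This endpoint is chosen as a surrogate endpoint of treatment efficacy, which is anticipated to correlate with long-term outcome".
- **The association analysis.** Under exploratory endpoint 4 in section 19.3.3, "The times from first ctDNA detection to recurrence event will be calculated using statistical techniques for time to event data" and the results are "summarised separately for patients with and without sustained ctDNA clearance". Then: "If numbers allow, time to recurrence will be formally compared between those with and without ctDNA clearance using standard time to event methods".

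Endpoint 4 names no landmark, no time-dependent covariate and no handling of recurrences before week 24. Section 1.1 does report a time-dependent covariate analysis and a Mantel-Byar test, but only for the earlier cohort.

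**The concern.** The grouping variable is known only at week 24 of treatment and contains the outcome, yet it is applied from a time origin before treatment starts. Every recurrence in the first 24 weeks is assigned to the non-clearers, and the clearers' curve stays at 100% over that time by construction. Sampling reinforces this: under section 13, ctDNA collection stops after the sample taken at recurrence, so an early recurrer cannot supply a week-24 negative.

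At stake is the interpretation of the primary endpoint. Clearance was chosen because it is expected to track long-term outcome, and endpoint 4 is the only listed analysis that relates the two directly. As written, a favourable result could not be told apart from the artefact.

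**Working it through.** The protocol gives no sample size, effect or power for this analysis, so there is no figure of its own to reproduce. The check asks what the planned comparison shows when the ctDNA result carries no information about recurrence.

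**Inputs**
- Patients treated: 30, the most likely row of the table in 19.1.2 (24 and 45 are its other rows).
- Landmark: 24 weeks / 4.345 = 5.52 months after first dose.
- Detection to first dose: 4 weeks, the maximum in 9.3, so 4 / 4.345 = 0.92 months. It is event-free for everyone who starts, because starting requires clear staging scans.
- Median time to recurrence: 7.1 months (the prior-cohort lead time in 1.1). 12 and 24 months are assumptions.
- Probability q of being ctDNA-negative at week 24, independent of recurrence: 0.5 and 0.3 (assumption, taking the values of p1 and p0 in 19.1.2).
- Follow-up of 24 months from detection and constant hazard (assumptions).

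**What the definition does before any test**

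Probability of being recurrence-free at week 24: S = 2^(−5.52/median). This gives 0.583 at 7.1 months and 0.727 at 12 months.

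Share of clearers = q × S. With q = 0.5 this is 0.29 and 0.36.

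Share of non-clearers who have already recurred by week 24 = (1 − S)/(1 − qS):
- median 7.1: 0.417/0.709 = 59%
- median 12: 0.273/0.636 = 43%

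Among clearers the share is 0% in both cases, although the ctDNA result is pure chance.

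**Simulation under this null** (5,000 trials per row, n = 30, log-rank at two-sided 5%)

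| Median (months) | q | Clearers | Planned: HR | Planned: false positives | Week-24 landmark: HR | Landmark: false positives |
|---|---|---|---|---|---|---|
| 7.1 | 0.5 | 0.29 | 0.48 | 44% | 1.01 | 7% |
| 12 | 0.5 | 0.36 | 0.53 | 30% | 1.02 | 6% |
| 24 | 0.5 | 0.43 | 0.57 | 17% | 1.01 | 6% |
| 7.1 | 0.3 | 0.18 | 0.58 | 18% | 1.02 | 7% |
| 12 | 0.3 | 0.22 | 0.62 | 12% | 1.00 | 6% |
| 24 | 0.3 | 0.26 | 0.65 | 7% | 0.97 | 5% |

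At an 18-month median with q = 0.5 the planned analysis gives a hazard ratio of about 0.55 and 22% false positives.

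**Sample size does not help.** With 45 treated and a 7.1-month median, false positives are 63% (q = 0.5) and 27% (q = 0.3). With 2,000 patients the hazard ratio is still 0.48 and 0.58, and every trial rejects.

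**A later clearance time is worse.** Exploratory endpoint 2 uses 12 months. With that definition, 30 patients, a 7.1-month median and 36 months' follow-up, the hazard ratio is 0.39 (q = 0.5) or 0.47 (q = 0.3), with 61% or 29% false positives.

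**Where the bias comes from.** The 24 treatment weeks drive it, not the interval from detection to first dose. That interval is event-free for both groups among patients who start. A log-rank test depends only on the order of event times, so a common shift of the origin changes nothing, and moving the clock to first dose would not cure the problem.

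**The case against.** The strongest points on the other side are these.

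1. **Weight.** This is the fourth exploratory endpoint, its formal test is conditional on numbers, and trial success rests on the A'Hern count in 19.1.2. The protocol does not claim that this analysis will validate surrogacy. That stands, and it is why the primary result is not in question.
2. **Size.** The larger figures need q near 0.5 and a constant hazard. Patients start with clear scans, and later imaging is done only if clinically indicated, so early recurrences may be fewer. With a rising hazard (Weibull shape 1.5, n = 30) false positives are 39%, 18% and 11% at medians of 7.1, 12 and 18 months for q = 0.5, and 16%, 7% and 6% for q = 0.3. With shape 2 they are 33%, 12% and 8%, and 14%, 7% and 5%. This stands as a statement of the range. It does not make the larger figures extreme: q = 0.3 implies overall clearance of only 0.18 to 0.26, below the design's unacceptable rate of 0.30, while clearance near the target of 0.5 pushes false positives at a 12-month median to just under 60%.
3. **SAP detail.** Section 19.4 leaves further methods to a SAP, and standard methods could include a landmark. This answers only part of the point. The protocol itself fixes the time origin and a grouping that contains the outcome, and the descriptive split, which is not conditional on numbers, is biased too.
4. **Cost of the remedy.** A landmark discards early recurrences, about 42% of patients at a 7.1-month median (1 − 0.583). True, but those events say nothing about what a week-24 result predicts.

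**Conclusion.** The concern holds. Followed as written, exploratory endpoint 4 favours clearers whether or not clearance has any prognostic meaning.

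The direction follows from the definitions alone. The size depends on assumptions the protocol does not fix. Under a constant hazard with 30 treated, the apparent hazard ratio under the null is 0.48 to 0.65 and the false-positive rate 7% to 44% across medians of 7.1 to 24 months and q of 0.3 to 0.5. A rising hazard lowers these figures, and clearance near the design target raises them. A week-24 landmark brings the hazard ratio to about 1 and the error rate to about 5 to 7%.

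The analysis should be changed before the data are examined. Primary and secondary results are unaffected.

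**What to change.** Replace the comparison in 19.3.3, endpoint 4, with the following.

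- **Main analysis.** Among patients who started pembrolizumab and are recurrence-free and under follow-up at week 24 from first dose, compare time from week 24 to recurrence by the week-24 ctDNA result alone (detected or not detected).
- **Support.** Fit a Cox model for recurrence from first dose with ctDNA status as a time-dependent covariate, updated at each 3-weekly sample and using only results obtained before the time at risk. This keeps the early recurrences.
- **Remove** the split by sustained clearance timed from first detection. Time from detection to recurrence is still reported by treatment group under exploratory endpoint 1.
- If the 12-month clearance definition is also related to recurrence, move the landmark to 12 months.

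No new data are needed. Section 10.1.1 has a pre-dose sample at every 3-week cycle, so a patient on schedule has one at week 24 (cycle 9, since 8 × 3 = 24). The change is a sentence in the protocol or SAP wording.

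The cost is information. At a 12-month median with 30 treated, about 30 × (1 − 2^(−23.08/12)) = 22 recurrences are expected by 24 months from detection. About 30 × 0.273 = 8 of them fall before the landmark, leaving about 14 among 22 patients. The landmark result should therefore be reported as an estimate with its confidence interval, and a non-significant result should not be read as no association.

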19.4. Statistical Analysis Plan

In the therapeutic component of the trial, analyses will be performed using the intention to treat (ITT) population meaning patients who do not meet the eligibility criteria (for reasons other than disease recurrence) or do not wish to receive pembrolizumab treatment will still be included in the analysis of the primary endpoint (ctDNA clearance). These patients should continue to have bloods taken for ctDNA surveillance every 3 months for up to 2 years from starting ctDNA surveillance. Patients will then be followed up until disease recurrence detection. Sensitivity analyses will also be performed using a per-protocol

population including only patients who start pembrolizumab treatment. If large differences are observed between ITT and per-protocol analyses, both results will be presented and reasons for failure to start pembrolizumab (ineligibility, patient choice) further explored.

All analysis will be repeated in the subset of patients who enter into the study within the recruitment time windows of protocol version 5.0, and the subset of patients who enter the study outside the recruitment time windows of protocol version 5.0. Further details of analysis methods will be specified in a Statistical Analysis Plan in accordance with ICR-CTSU Standard Operating Procedures.

The Statistical Analysis Plan will include a section to detail how data impacted by strategies introduced to mitigate risks relating to the COVID-19 pandemic will be handled.

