1.2.1. Rationale for study design

Selection of patients for treatment on the basis of a positive ctDNA test

Although assays of MRD are standard in the management of haematological cancers, this will be one of the first studies to assess whether ctDNA assays have clinical utility in guiding further therapy. Patients recruited into the c-TRAK TN study will be of moderate or high risk of future relapse. The inclusion criteria, on which risk for relapse are based, are similar to many previous adjuvant therapy studies for breast cancer (for example, BEATRICE NCT00528567 [16]) that have randomised all patients unselected to treatment or placebo. However, in these studies many patients never relapse, are consequently treated unnecessarily, and do not contribute to the primary endpoint of the study. In c-TRAK TN we will use assays of ctDNA to further select from within this population a set of patients who are at very high risk of relapse (i.e. those with a positive ctDNA test).

Prior to the implementation of protocol v6.0 during the original randomised component of the trial, this high risk population was randomised between intervention with medicinal product or observation. The standard of care for these patients is observation, and no treatment will be withdrawn as a result of ctDNA testing.

In protocol version 6.0, following recommendations made by the c-TRAK TN IDMC (further detail provided in the paragraph below), the trial design changed into the non-randomised component; randomisation was removed and all patients with a positive ctDNA result will be allocated to intervention with pembrolizumab. Patients who were previously randomised to observation and are continuing with ctDNA surveillance, will be asked to re-consent and subsequently be allocated to pembrolizumab at the next positive ctDNA test.

Rationale for the change in study design – June 2020 (protocol v6.0)

Study progress to date has provided data enhancing the evidence that ctDNA presence in the blood of patients treated for moderate and high risk TNBC is a definitive positive predictor of disease recurrence. In addition to this, data from external sources and emerging data from this trial suggest that instances of overt metastatic disease in these patients presents more frequently than initially predicted at study onset, that

c-TRAK TN Protocol

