3.2.1. Pembrolizumab treatment group

If a patient is allocated to the pembrolizumab treatment group, the treating team will be informed by ICR-CTSU. If the patient is receiving adjuvant capecitabine or radiotherapy, they will be offered the option to join the therapeutic trial either by switching treatment from capecitabine to pembrolizumab, or commencing pembrolizumab in combination with radiotherapy. If the patient confirms their consent to receive trial treatment (including switching their treatment from capecitabine to pembrolizumab) staging scans should be done to detect for evidence of macroscopic disease, prior to commencing pembrolizumab. If macroscopic disease is detected, the patient will not receive pembrolizumab treatment and will instead receive standard treatment for recurrent disease outside of the c-TRAK TN trial. If there is no evidence of macroscopic disease, the patient should commence treatment with pembrolizumab treatment (200mg given intravenously every 3 weeks) for up to a maximum of 12 months or until unacceptable toxicity or withdrawal of the patient's consent for any reason (see section 11.6). No further imaging will be performed after commencing pembrolizumab unless clinically indicated, in which case local procedure should be followed. Patients who are diagnosed with disease recurrence must stop pembrolizumab, and should receive standard treatment for recurrent disease outside of the c-TRAK TN trial. Patients who present with isolated lymphadenopathy may continue pembrolizumab until relapse is confirmed, and should be managed as per section 13.1.

Patients who are allocated to pembrolizumab but do not wish to commence pembrolizumab treatment (including switching treatment from capecitabine to pembrolizumab), will not enter the therapeutic component of the c-TRAK TN trial and if agreed should instead continue with 3 monthly ctDNA surveillance. Blood samples for ctDNA analysis should continue to be collected during and after pembrolizumab treatment as described in section 11. The results of these ctDNA analyses will not be reported to the treating team or patient.

3.2.2. **Observation group (continued blinded ctDNA surveillance – prior to protocol v6.0)**

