19.1.2. Therapeutic component

Under the original randomised study design (prior to protocol v6.0), those patients allocated via randomisation to observation provide a reference control rather than a formal randomised comparator group. The statistical considerations underpinning the therapeutic intervention evaluation are those of a single group trial with patients treated with pembrolizumab in both the randomised and non-randomised

trial components combined. The original design hypothesised frequencies of ctDNA+ and allocation to pembrolizumab as per the text and table outlined below. The revision in the design to close the randomised component has the potential to increase the number of patients commencing pembrolizumab. No redefinition of the criteria have been undertaken since the success criteria are determined by the number starting treatment and not the overall proportion available to receive treatment.

The rate of ctDNA positivity is prone to stochastic effects, and as such a range of effect sizes is presented. All patients in the screening cohort who are observed to have a positive ctDNA will be entered into the therapeutic component, therefore the eventual number entering that phase will only be defined as the trial progresses. The most likely incidence, on which the primary calculations were made, is for a 30% positivity rate during the first 12 months. Calculations use an A'Hern single-stage design within pembrolizumab treated patients, alpha=0.1, power=90%, unacceptable ctDNA clearance rate p0 (of 0.3) and minimum required level of efficacy p1 of approximately 0.5. The number of clearances to conclude the required level of success and width of the 95% confidence interval which could be detected around a proportion with ctDNA clearance of approximately 0.5 are given for each hypothesised rate of ctDNA positivity.

Rate of ctDNA positivity	No. ctDNA positive (of 150 in ctDNA surveillance phase)	No. randomised to receive pembrolizumab	р0	р1	No. successes required	Width of 95% confidence interval detectable around proportion of 0.5
45%	68	45	0.30	0.49	18	+/- 0.14
30%	45	30	0.30	0.54	13	+/- 0.17
24%	36	24	0.30	0.57	10	+/- 0.19

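### Protocol section 19.4 puts patients who never start pembrolizumab into the primary clearance analysis, while sections 19.1.2, 19.3.1 and 3.2.1 define the test, its clock and trial entry by starting treatment; which number sets the threshold is left open

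*Protocol*

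**What the plan says.** Four places in the protocol bear on who is in the primary therapeutic test.

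- **Section 19.1.2 (design).** The calculation is an "A'Hern single-stage design within pembrolizumab treated patients". On the change made in v6.0 it adds that "the success criteria are determined by the number starting treatment and not the overall proportion available to receive treatment". The table beneath, however, takes its n from a column headed by the number randomised to pembrolizumab.
- **Section 19.3.1 (endpoint).** The result is "the proportion of patients without either detectable ctDNA or disease recurrence 6 months after commencing pembrolizumab".
- **Section 3.2.1 (entry).** Patients who are allocated pembrolizumab but decline it "will not enter the therapeutic component of the c-TRAK TN trial"; if they agree, they go on with three-monthly surveillance.
- **Section 19.4 (analysis).** The therapeutic analysis is by intention to treat. Patients found ineligible on grounds other than relapse, and those who "do not wish to receive pembrolizumab treatment will still be included in the analysis of the primary endpoint (ctDNA clearance"). Patients who start form a per-protocol sensitivity population. If the two analyses differ greatly, both are to be presented.

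**The concern.** The population for which alpha and power were worked out is the one that section 19.4 demotes to a sensitivity analysis. The patients it adds have no start date, so an endpoint counted from the start of pembrolizumab has no origin for them. Their blood schedule differs too: every three months counted from the start of surveillance (section 19.4), against every three weeks on treatment (section 10.1.1). Section 19.4 does not say whether they count as failures or are assessed at some other date.

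A single-arm rule is a pair, n and r. If it is not fixed whether n is the number allocated or the number starting, the same data can pass under one reading and fail under the other. Section 19.4 does not say which result then decides. Non-starting is foreseeable: section 9 provides for refusal to switch from capecitabine, and section 19.3.2 makes starting treatment a secondary endpoint.

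**Working it through.** **Inputs from the protocol (section 19.1.2).** p0 = 0.30; alpha 0.1; power 90%; table rows n = 45, p1 = 0.49, r = 18; n = 30, p1 = 0.54, r = 13; n = 24, p1 = 0.57, r = 10. The same section reports that no patient with ctDNA at baseline cleared spontaneously in prior research.

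**Assumptions.** The protocol gives no share of allocated patients who will not start, so about 10%, 20% and 30% are shown. The clearance rate q in never-starters is taken as 0, following the prior research, and as 0.05 or 0.10 for sensitivity.

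**Formulas.** With X ~ Binomial(n, p), alpha = P(X ≥ r | p0) and power = P(X ≥ r | p1). With s starters and u never-starters, the number of successes is Binomial(s, p) + Binomial(u, q).

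**Step 1: the plan's own rules, everyone starting.**
- 13/30: alpha 0.0845, power 0.912 at 0.54.
- 18/45: alpha 0.0986, power 0.913 at 0.49.

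Both reproduce the stated design.

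**Step 2: reading A. The threshold follows the number allocated and never-starters count in n.** With q = 0, successes come from starters alone, so the probability is P(X ≥ r) with X ~ Binomial(s, p).

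| Allocated, r | Not starting | Starters | Alpha | Power |
|---|---|---|---|---|
| 30, 13 | 3 | 27 | 0.036 | 0.789 |
| 30, 13 | 6 | 24 | 0.012 | 0.577 |
| 30, 13 | 9 | 21 | 0.002 | 0.308 |
| 45, 18 | 4 | 41 | 0.041 | 0.791 |
| 45, 18 | 9 | 36 | 0.009 | 0.518 |

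With q = 0.10 the three 30-patient rows have power 0.816, 0.661 and 0.457, and alpha no higher than 0.050.

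**Step 3: reading B. The threshold follows the number starting; never-starters are added to the analysis.** Take r = 13, set by 30 starters.
- q = 0: the success count is unchanged, so alpha stays 0.0845 and power 0.912.
- 6 added, q = 0.05: alpha 0.108.
- 6 added, q = 0.10: alpha 0.135.
- 9 added, q = 0.10: alpha 0.164.

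**Step 4: can the readings disagree on the same data?** Take 30 allocated, 24 starting and q = 0. For n = 24 the smallest r that keeps alpha at or below 0.1 is 11 (alpha 0.074). So 11 or 12 clearances succeed against 11/24 and fail against 13/30. At p = 0.54:

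P(X ≥ 11) − P(X ≥ 13) = 0.843 − 0.577 = 0.27 (rounded).

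The table's 24-patient row prints r = 10, which has alpha 0.153. That is a separate matter; 11 is used here so that both rules respect the stated alpha.

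**The case against.** The strongest reply is that section 19.1.2 already answers the question. It ties the criteria to the number starting, so with 24 starters the threshold is not 13. An A'Hern rule counts successes, so never-starters who do not clear alter neither the count nor r, and alpha and power are as stated. The table header can be read as wording kept from the randomised design, and section 19.5 has the IDMC settle the relevant criteria as numbers emerge. An all-allocated primary analysis is also defensible and conservative, a starters-only analysis is already promised, and the SAP could supply the missing clock; section 19.3.2 times the observation group from randomisation, which is a precedent.

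Much of this stands. The power loss is conditional on reading A, and keeping the all-allocated population is a legitimate choice. What does not fall away is that the protocol contradicts itself on who is in the decisive analysis, and that the harmless reading still needs an unstated rule that never-starters count as failures.

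Three stronger inferences are not supported.

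- A reader might infer that alpha is breached. In reading A, for the 30- and 45-patient rows, it falls. It passes 0.10 only in reading B, and only if enough never-starters are counted as clear.
- A reader might infer that patients barred by macroscopic disease on staging dilute the analysis, since section 1.2.1 says that "instances of overt metastatic disease in these patients presents more frequently than initially predicted at study onset". Section 19.4 limits its inclusion of ineligible patients to grounds other than relapse, so these patients lower n and do not add failures.
- A reader might treat a smaller number of starters as a power defect in itself. The table lets p1 rise as n falls (0.49, 0.54, 0.57), so a larger detectable effect at smaller n is part of the design. For example, 11/24 has power 0.843 at 0.54 but 0.905 at the 0.57 given for that row.

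**Conclusion.** The inconsistency is real and concerns the primary therapeutic question. Section 19.4 cannot be applied together with sections 19.1.2, 19.3.1 and 3.2.1 as written: the patients it adds have no clock, and two values of n compete to set the threshold.

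The size depends on the reading. If r follows the number allocated and never-starters do not clear, power drops from about 0.91 to 0.79, 0.58 or 0.31 with 10%, 20% or 30% of 30 not starting, and to 0.79 or 0.52 with 4 or 9 of 45 not starting; the test is then conservative. If r follows the number starting, the stated figures hold unless some never-starters are counted as clear. With 24 of 30 starting, a conflict between the two decisions has probability 0.27 at a true clearance rate of 0.54. The non-start rates are assumptions. The stated alpha and power do hold for the starters-only analysis in the 30- and 45-patient rows.

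**What to change.** Name one population for the A'Hern decision and align sections 19.1.2, 19.3.1, 19.4 and 3.2.1 with it.

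- **Option that fits the design as calculated: patients who start pembrolizumab.** Relabel the table's n column as the number starting, set r by the exact binomial rule for the n that actually start, and report the all-allocated analysis as supportive, timed from allocation. The 30- and 45-patient rows keep their stated alpha and power.
- **If intention to treat stays primary.** Define the origin of the 24-week clock for patients who never start, state how they are counted, index r to that same n, and restate power over a range of non-start rates such as the one above.

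Either way, say which analysis decides if the two disagree. The cost is protocol and SAP wording, with no new data or visits, but the choice must be made before clearance results are known. The second option also means publishing a lower power.
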